2.5.2 Baseline values

In general, the baseline value of an analysis variable is defined as the last observation before the first dose of the treatment.

2.5.3 Data handling conventions for secondary efficacy variables

Valid/Evaluable tumor assessment:

A valid post-baseline tumor assessment is one for which the derived “overall objective response” is not “NE” (not evaluable) as per RECIST 1.1 criteria. If the date of assessment is missing, the tumor assessment is not valid.

In case of missing scans, i.e. if one lesion is not evaluated/missing for a given tumor assessment, the overall response should generally be NE unless there is a clear evidence of progression (independently of the missing lesion).

Date of last valid tumor assessment (different from PD): if several scans are performed at different dates for a given tumor evaluation reported in the e-CRF, the date of the last valid tumor assessment is the date of latest scan.

Date of disease progression determination:

- PD by New lesion: for progression based on a new lesion, the date of progression is the date of the first observation that the new lesion was detected,
- PD by target lesion: if multiple assessments based on the sum of target lesion measurements are done at different times, the date of progression is the date of the first radiological measurement,
- PD by non-target lesion: if the first documented progression is based on a non-target lesion alone, the date of PD is the initial date at which unequivocal progression is associated with non-target disease,

- PD by a combination of factors: if the first documented progression is based on a combination of target and new and/or non-target disease, the date of PD shall be the earliest date associated with any of the contributing factors.

The rules to determine date of progression are consistent with FDA recommendation described in “Guidance for Industry Clinical”

- Efficacy response variable: when a proportion is calculated for a binary response variable (eg, response rate), the denominator is based on the total number of patients in the analysis population used for the summary. There can be 3 observations: Yes, No and Nonevaluable (or missing). For the patients with non-evaluable outcomes, the default rule is that the patients will be treated as “no events”.
- Time to event data: missing outcomes due to different reasons will be handled using adequate censoring rules. The censoring rules are specified as part of the definition of the analysis variables in corresponding section.
- Handling of missing/partial death dates:
 - If the day of the death date is missing, it will be imputed as the first day of the month, except if the date of the patient's last contact is in the same month as the death date. In this case, the death date is imputed as the date of last contact + 1 day.
 - If the day and month of the death date is missing, the date of death will be imputed to the first of January of the year, except if the date of the patient's last contact is in the same year as the death date. In this case, the death date will be imputed as the date of last contact + 1 day.
 - If the death date is missing, no imputation will be done and the patient will be censored at the last contact date.
- Incomplete date of first post-treatment anti-cancer therapy: if the day of first post-treatment anti-cancer therapy is missing, the date will be imputed to the first day of the month.

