9 ASSESSMENT OF INVESTIGATIONAL MEDICINAL PRODUCT

9.1 PRIMARY ENDPOINTS

9.1.1 Primary safety endpoint for Part 1

- Incidence of IMP-related predefined safety criteria during Cycle 1 and Cycle 2.

Predefined safety criteria are defined at the occurrence of any following related TEAE using NCI CTCAE v4.03:

- Grade ≥ 3 TEAE from the System Organ Class (SOC) Eyes disorders,
- Grade ≥ 3 peripheral neuropathy (Preferred Term [PT]),
- Grade ≥ 4 TEAE.

9.1.2 Primary efficacy endpoint for Part 1 and Part 2

The primary efficacy endpoint in Part 1 and Part 2 is ORR (proportion of patients with CR or PR as best overall response [BOR]) according to RECIST 1.1 ([Appendix A](#)), assessed by the Investigator. Confirmation of objective responses will be performed by repeat tumor imaging (Computed Tomography [CT] scan, MRI) at least 4 weeks after the first radiological documentation of response.

Tumor assessments will be performed until disease progression, even if the patient has discontinued study treatment before documented disease progression, or study cut-off date, whichever comes first.

The same imaging techniques should be used from baseline to disease progression to maintain consistency. If contrast agent is used at baseline, it must be used for all subsequent evaluations. Ultrasound is not permitted for evaluation of tumor progression.

Baseline imaging evaluations are to be performed within 21 days of the first study treatment administration. A chest and abdominal CT or MRI scan, or other relevant examinations as clinically indicated, are requested.

At each time point, evaluations must consist of a chest and abdominal CT or MRI scan and any other exams as clinically indicated.

Disease progression will be determined by at least a 20% increase in the sum of diameters of target lesions, taking as reference the smallest sum on study (this includes the baseline sum if that is the smallest on study). In addition to the relative increase of 20%, the sum must also demonstrate an absolute increase of at least 5 mm. The appearance of 1 or more new lesions or an unequivocal increase in the size of nontarget lesions is also considered as progression.

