Appendix B Determination of tumor response

The overall response at each time point and the best overall response will be determined by the Investigator derived from the tumor measurements data according to RECIST 1.1 criteria ([Appendix C](#)) using the following algorithm.

- Overall Response:

Overall response, or integrated response, will be determined by the investigator using assessments of target, non-target and new lesions according to RECIST 1.1. See [Appendix C](#) for details.

- Confirmation:

According to RECIST 1.1 a confirmed CR or PR will be based on two tumor assessments at least four weeks apart as follows: if a CR or PR outcome is reported, then a second tumor assessment with CR or PR at least four weeks later is needed for confirmation, regardless of how many “unknown/not applicable/missing/non evaluable” tumor assessments are in between the two outcomes.

- Best Overall Response (BOR) :

In general, a patient’s best tumor response will depend on the achievement of both: documented tumor measurement assessments and confirmation of the tumor response by RECIST1.1 criteria. For each patient the BOR will be derived based on the following algorithm:

– a) PR/CR will be determined based on confirmed PR and confirmed CR described in the algorithm above.

– b) SD and PD will be determined from the overall tumor response at each timepoint. If SD is the overall response and it occurs less than 35 days from first study administration, then overall response will not be SD. For patients who stop the treatment due to a symptomatic deterioration or death, without any other tumor assessment before the symptomatic deterioration or death, then the BOR will be considered as NE. These cases will be described separately as patients in early progression or early death.

If PD is the overall response and it occurs less than 42 days from the first study administration, then the best overall response is PD.

– c) Convention for PD after several NE cycles: in the case where the assessment at study entry is followed by several visits (or cycles) with no assessment (or only NE assessments or SD <35 days from first study administration) for more than twice the periodicity of tumor assessments (ie, for more than 42 days), and the next assessment is PD, the best overall response will be NE. If the PD occurs within this period of time, the best overall response will be PD.

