Although a clear progression of "non target" lesions only is exceptional, in such circumstances, the opinion of the treating physician. Should prevail and the progression status should be confirmed later on by the review panel (or study chair).

Evaluation of Best overall response

It is assumed that at each protocol specified time point, a response assessment occurs. The following table provides a summary of the overall response status calculation at each time point for patients who have measurable disease at baseline.

Table 18 - Evaluation of overall response

Target lesions	Non-target lesions	New lesions	Overall response
CR	CR	No	CR
CR	Non-CR/non-PD	No	PR
CR	Not evaluated	No	PR
PR	Non-PD or not all evaluated	No	PR
SD	Non-PD or not all evaluated	No	SD
Not all evaluated	Non PD	No	NE
PD	Any	Yes or No	PD
Any	PD	Yes or No	PD
Any	Any	Yes	PD

Table 19 - Evaluation of best overall response

Overall response	Overall response		BEST overall response
	First time point	Subsequent time point	
CR	CR	CR	CR
CR	PR	PR	SD, PD or PR ^a
CR	SD	SD	SD provided minimum criteria for SD duration met, otherwise, PD
CR	PD	PD	SD provided minimum criteria for SD duration met, otherwise, PD
CR	NE	NE	SD provided minimum criteria for SD duration met, otherwise NE
PR	CR	CR	PR
PR	PR	PR	PR
PR	SD	SD	SD
PR	PD	PD	SD provided minimum criteria for SD duration met, otherwise, PD
PR	NE	NE	SD provided minimum criteria for SD duration met, otherwise NE
NE	NE	NE	NE

^a If a CR is truly met at first time point, then any disease seen at a subsequent time point, even disease meeting PR criteria relative to baseline, makes the disease PD at that point (since disease must have reappeared after CR). Best response would depend on whether minimum duration for SD was met. However, sometimes 'CR' may be claimed when subsequent scans suggest small lesions were likely still present and in fact the patient had PR, not CR at the first time point. Under these circumstances, the original CR should be changed to PR and the best response is PR.

The best overall response is determined once all the data for the patient is known.

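### SAP 2.5.3 makes a time point NE when any lesion is missing, while the RECIST tables keep PR or SD when only a non-target lesion is missing; valid-assessment dates, DCR and censoring depend on which is followed

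*SAP*

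**What the plan says.** SAP 2.5.3 carries the title "Data handling conventions for secondary efficacy variables". It defines a valid post-baseline assessment as one whose derived overall response is not NE under RECIST 1.1. It then adds that, where scans are missing, "if one lesion is not evaluated/missing for a given tumor assessment, the overall response should generally be NE". The one stated exception is clear progression that does not depend on the missing lesion. The sentence does not say whether the lesion is target or non-target.

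SAP Appendix C Table 18 and protocol Appendix A Table 3 are the same table, and both make that distinction. In the PR and SD rows the non-target entry reads "Non-PD or not all evaluated", and the overall response remains PR or SD. Target CR with non-target lesions not evaluated gives PR. The only NE row is the one where the target lesions are incompletely evaluated.

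For the primary endpoint, SAP 2.1.3.1 sends the reader to Appendix B. That appendix says "Overall response, or integrated response, will be determined by the investigator using assessments of target, non-target and new lesions according to RECIST 1.1" and refers to Appendix C for detail. If a CR or PR is reported, "then a second tumor assessment with CR or PR at least four weeks later is needed for confirmation", however many non-evaluable scans fall in between.

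On imaging, protocol 9.1.2 says that at each time point "evaluations must consist of a chest and abdominal CT or MRI scan and any other exams as clinically indicated".

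**The concern.** For a missing target lesion the two rules agree. For a missing non-target lesion they give different answers for the same scan: PR or SD under the tables, NE under 2.5.3. No precedence is stated. Section 2.5.3 also conflicts with its own definition of validity, which rests on RECIST 1.1.

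The situation can occur. The named minimum imaging is chest and abdomen, so a non-target lesion elsewhere, for example in bone or brain, may go unimaged at a follow-up visit.

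Whether a time point is NE feeds several definitions:

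- the last valid assessment, which sets censoring for DOR (SAP 2.1.3.2.1), TTP (2.1.3.2.3) and PFS (2.1.3.2.4);
- the duration of stable disease, and so DCR (2.1.3.2.2);
- membership of the response evaluable population (2.3.1.2), if the same NE rule is used there.

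Two programmers following the SAP in good faith could report different DCRs and different censoring times from the same data.

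**Working it through.** **1. The rules side by side**

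| Target | Non-target | New lesion | Table 18 / protocol Table 3 | SAP 2.5.3 |
|---|---|---|---|---|
| CR | not evaluated | no | PR | NE |
| PR | some missing, rest non-PD | no | PR | NE |
| SD | some missing, rest non-PD | no | SD | NE |
| some missing | non-PD | no | NE | NE |
| PD | any | any | PD | PD (by the exception) |

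The first three rows conflict and the last two agree. Because progression is exempt, 2.5.3 does not remove PFS or TTP events. It affects valid-assessment dates, stable disease and response.

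**2. Constructed patients.** Scans are every 6 weeks, as the protocol schedules them, with no new lesion before any PD. A missed scan means that one non-target lesion was not evaluated.

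- *DCR.* Target SD at weeks 6 and 12, non-target missed both times, PD at week 18. Table 18 gives SD, SD, PD. Stable disease lasts 18 × 7 = 126 days, which exceeds 3 months, so the patient counts as disease control. Under 2.5.3 the sequence is NE, NE, PD. Appendix B item (c) then gives BOR NE, since 126 days exceeds both the printed 42 days and the 84 days that twice a 6-week interval would be. The patient does not count.
- *DOR and PFS censoring.* PR with all lesions evaluated at weeks 6 and 12, then target PR with non-target missed at weeks 18 and 24. No progression, death or new therapy by cut-off. Table 18 censors DOR at 24 − 6 = 18 weeks and PFS at week 24. Under 2.5.3 the last valid scan is week 12, so DOR is censored at 12 − 6 = 6 weeks and PFS at week 12.
- *Day 1 censoring.* Target SD at weeks 6 to 24, non-target never re-imaged, no progression or death. Table 18 censors PFS at week 24. Under 2.5.3 there is no valid assessment, and SAP 2.1.3.2.4 censors on Day 1. If the same NE rule is applied to SAP 2.3.1.2, this patient also leaves the response evaluable population.
- *Response.* Target PR at weeks 6 and 12, non-target missed both times, PD at week 18. Table 18 gives a confirmed PR. Under 2.5.3 the sequence is NE, NE, PD and BOR is NE. If only the middle of three PR scans (weeks 6, 12, 18) is affected, the response is confirmed under both rules, because weeks 6 and 18 are more than four weeks apart.

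**3. Illustration for ORR.** This step applies only if 2.5.3 is also used to derive the primary endpoint.

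Inputs from SAP 1.3.2 and section 3: null rate 12%, alternative 30%; stop at 0–1 of 14; reject at 6 or more of 14; otherwise reject at 7 or more of 29. With X the responses among the first 14 and Y those among the next 15,

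Power(p) = P(X ≥ 6) + Σ over x = 2 to 5 of P(X = x) · P(Y ≥ 7 − x).

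At p = 0.30 this gives 0.8004, which reproduces the stated 80%. At p = 0.12 it gives 0.0501, within the stated 10%.

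At the final boundary, 7/29 (24.1%) gives one-sided p = 0.052 with 80% CI 14.0–37.2%, and 6/29 (20.7%) gives p = 0.127 with 80% CI 11.2–33.5%.

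Let q be the share of true responders who become non-responders, so p = 0.30(1 − q). The documents give no value for q; the values below are assumptions.

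| q | p | Power | P(X ≤ 1 of 14) |
|---|---|---|---|
| 0 | 0.300 | 80.0% | 4.7% |
| 5% | 0.285 | 74.9% | 6.0% |
| 10% | 0.270 | 69.0% | 7.5% |
| 20% | 0.240 | 55.2% | 11.6% |

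**The case against.** The best defence is that 2.5.3 is a loose summary subordinate to RECIST. It says the response should generally be NE, not always, and the paragraph before it ties validity to RECIST 1.1. A careful programmer might therefore go to Table 18. That is a sensible reading, but the text does not require it, and the only exception it names is progression.

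Missed non-target lesions should also be uncommon. Protocol 10.1.4 asks that all target and non-target lesions be assessed on treatment with identical techniques, and Appendix A asks for the same method for each lesion throughout. This stands: a missed lesion would usually depart from those instructions, and nothing in the documents gives a frequency. Still, 2.5.3 exists because missing scans are expected.

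A reader might infer that the conflict governs the primary analysis and that the power losses above are expected. The documents do not support that. The rule sits under a heading for secondary variables, and ORR has its own route through Appendix B to Table 18. A single NE scan does not lose a response while two CR/PR scans at least four weeks apart remain. The one-patient margin at 7/29 or 2/14 would apply to any classification doubt, so it does not measure this one.

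The separation is not complete, however. Section 2.5.3 also contains the response-rate denominator rule, which counts non-evaluable patients as non-events, so its NE rule could be carried into ORR. Reading the heading strictly creates a different problem: the last patient in step 2 who lost the response would be a confirmed responder for ORR but not for DCR, although DCR is defined to include confirmed CR and PR.

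**Conclusion.** Wrong as written. SAP 2.5.3 contradicts SAP Table 18 and protocol Appendix A Table 3 whenever only a non-target lesion is unevaluated and there is no progression, and no order of precedence is given.

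Following 2.5.3 literally affects secondary endpoints directly. Valid-assessment dates move earlier, some stable disease is lost from DCR, and DOR, TTP and PFS are censored too early, at worst on Day 1 for PFS. For an affected patient the shift can be the whole of follow-up. The number of such patients cannot be estimated from the documents.

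An effect on the 2/14 or 7/29 decision is possible but conditional. It needs 2.5.3 to be applied when the time-point response for ORR is derived, and a patient left without a confirming pair of scans. The fall in power from 80.0% to 74.9%, 69.0% or 55.2% rests on both conditions and on assumed losses of 5%, 10% and 20% of responders. It illustrates a possible effect and does not forecast one. The sample size and decision rules need no change.

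**What to change.** In SAP 2.5.3:

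- Limit the NE rule to missing target lesions: if one or more target lesions are not evaluated, the overall response is NE unless progression is evident.
- State that Table 18 applies when only non-target lesions are not evaluated and there is no new lesion: target CR gives PR, PR gives PR, SD gives SD.
- State that a single time-point response derived from Table 18 serves BOR and ORR, DCR, the response evaluable population, and all valid-assessment and censoring dates.

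The cost is two or three sentences and one programming condition. No new data are needed, and the change is best made before the Part 1 interim analysis is programmed.

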2.1.3.2 Secondary efficacy endpoint(s)

The secondary efficacy endpoints include duration of response (DOR), Disease Control rate (DCR), Time to progression (TTP) and Progression Free Survival (PFS).

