2.1.3.2.1 Duration of response

The duration of response will be defined as the time from the date of first initial occurrence of a subsequently confirmed CR or PR to the date of first radiological documentation of disease

progression (using RECIST 1.1) before the initiation of any post-treatment anti-cancer therapy or death (due to any cause), whichever occurs first.

Duration of response is determined only for patients who have achieved a response of confirmed CR or PR.

If a patient receives post-treatment anti-cancer therapy before radiologic progression or death, the duration of response will be censored at the date of the last valid response assessment without evidence of progression performed before the initiation of the post-treatment anti-cancer therapy.

If a patient receives post-treatment anti-cancer therapy without radiologic progression or death, the duration of response will be censored at the date of the post-treatment anti-cancer therapy.

In the absence of radiologic progression, death or post-treatment anti-cancer therapy, the duration of response will be censored at the date of the last valid response assessment without evidence of progression.

A valid response assessment is defined as a response assessment with a response different of NE.

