2.1.3.2.4 Progression-free survival

Progression-Free Survival (PFS) is defined as the time interval from the date of the first treatment infusion to the first documented date of disease progression or death due to any cause, whichever occurs first.

Rules for sensitivity analysis

PFS endpoint will be determined considering also clinical/non radiological progression as an event. If clinical/non radiological progression is observed in absence of documented radiological progression, the date of progression will be the date of clinical/non radiological progression. If the first progression is based on documented radiological progression and on clinical/non radiological progression, the date of progression will be the earliest of date of documented progression and date of clinical/non radiological progression.

Censoring rules for all PFS analyses:

For these 2 analyses, in the absence of disease progression or death (or clinical/non radiological progression for sensitivity analysis), the PFS will be censored at the date of last evaluable tumor assessment without documented progression. In addition, the patient without any valid post-baseline tumor assessment will be censored for PFS on the day of the first study treatment infusion (Day 1).

The summarized description of these analyses is given in [Appendix F](#).

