Appendix F Description of primary and sensitivity analyses of PFS

Table 20 - PFS Primary analysis

Situation	Date of progression or censoring	Outcome
No baseline tumor assessments	Date of first treatment administration	Censored
Documented progression according to investigator	Earlier of: - Date of radiological assessment showing new lesion or progression of non-target lesion - Date of last radiological assessment of target lesions (if progression is based on increase in sum of target lesions)	Event
Death without documented progression according to investigator	Date of death	Event
Both documented progression according to investigator and death	Date of progression	Event
No documented progression according to investigator and no death	Date of last valid tumor assessment without evidence of progression	Censored
Symptomatic deterioration reported and no documented progression according to investigator and no death	Ignored	Ignored
Initiation of new anti-cancer treatment	Ignored	Ignored

Table 21 - PFS sensitivity analysis #1 (progression based on investigator's assessment of lesions, and including symptomatic deterioration)

Situation	Date of progression or censoring	Outcome
No baseline tumor assessments	Date of first treatment administration	Censored
Documented Progression (without symptomatic deterioration) according to the investigator	Earlier of: - Date of radiological assessment showing new lesion or progression of non-target lesion - Date of last radiological assessment of target lesions (if progression is based on increase in sum of target lesions)	Event
Death without documented progression and without symptomatic deterioration	Date of death	Event
Symptomatic deterioration reported with no documented progression according to investigator and no death	Date of symptomatic deterioration	Event
Symptomatic deterioration and documented progression according to the investigator regardless of death occurrence	Earlier of the date of symptomatic deterioration and date of progression	Event
Symptomatic deterioration and death with no documented progression according to the investigator	Date of symptomatic deterioration	Event
Documented progression according to the investigator and death with no symptomatic deterioration	Date of progression	Event
No progression according to the investigator, no death, and no symptomatic deterioration	Earlier of the date of last valid tumor assessment without evidence of progression and cut-off date	Censored

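### SAP 2.5.3 censors a known death with no date at the last contact date, although death without earlier documented progression is a PFS and DOR event and no SAP endpoint censors at last contact

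*SAP*

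**What the plan says.** SAP 2.5.3 has a set of rules for missing or partial death dates, so it deals with patients already known to be dead.

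- **Day missing:** the date is imputed to the first of the month, or to last contact + 1 day if last contact was in that month.
- **Day and month missing:** it is imputed to 1 January, unless last contact was in that year: "In this case, the death date will be imputed as the date of last contact + 1 day".
- **Whole date missing:** "If the death date is missing, no imputation will be done and the patient will be censored at the last contact date".

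The same section says of time-to-event data: "The censoring rules are specified as part of the definition of the analysis variables in corresponding section". Those definitions read as follows.

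- **PFS (SAP 2.1.3.2.4)** runs "to the first documented date of disease progression or death due to any cause, whichever occurs first". Only when neither event has occurred does the general rule apply: "the PFS will be censored at the date of last evaluable tumor assessment without documented progression". A patient with no valid post-baseline assessment is censored at Day 1.
- **PFS, Table 20 (SAP Appendix F)** has a row "Death without documented progression according to investigator", with outcome event at the date of death. Its row for censoring at the last valid assessment requires that there was no death.
- **DOR (SAP 2.1.3.2.1)** counts death from any cause. With no progression, death or new therapy, "the duration of response will be censored at the date of the last valid response assessment without evidence of progression".
- **TTP (SAP 2.1.3.2.3)** counts death from disease progression and censors other deaths at the last evaluable assessment.

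The SAP has no overall-survival endpoint.

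**The concern.** Censoring at last contact is the usual convention for overall survival, which this SAP does not analyse. Applied to PFS, DOR and TTP it does two things. It turns an outcome that the definitions call an event into a censored observation, for a reason that is itself the outcome. And it stops the clock at a date that none of the three definitions uses, although SAP 2.5.3 says that the censoring rules sit in those definitions.

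It also makes the handling of death dates discontinuous. With only the year known, the patient is an event; lose the year as well, and the same patient becomes a non-event.

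At stake is a modest overstatement of Kaplan-Meier PFS, DOR and TTP, and an inconsistency that would otherwise be settled during programming, after data have been seen.

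**Working it through.** The documents give no figure on this point, so there is nothing to reproduce. The check is a comparison of texts, followed by an illustration of size.

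**1. Censoring dates the SAP allows**

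| Endpoint | Does death count as an event? | Censoring dates in the definition |
|---|---|---|
| PFS, primary | Yes, any cause | Last valid assessment; first infusion if there is no baseline or no valid post-baseline assessment |
| PFS, sensitivity | Yes, any cause | As above, or cut-off date if earlier |
| DOR | Yes, any cause | Last valid assessment; date of new anti-cancer therapy |
| TTP | Yes, if from progression | Last valid or evaluable assessment; date of new anti-cancer therapy |

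Last contact is in no row. The planned summaries of censoring time (SAP 2.4.4.2.4 and 2.4.4.2.5) name randomization and last disease assessment, not last contact.

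**2. One patient (invented example).** Last scan Day 84, stable disease; last contact Day 120; known dead, no date; no documented progression.

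- Whole-date rule in SAP 2.5.3: censored at Day 120.
- Neighbouring convention (last contact + 1 day): event at Day 121.
- General PFS censoring date, if it applied to a dead patient: Day 84.

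**3. When an event is really lost.** If progression was documented first, Table 20 already places the PFS event at the progression date, and nothing should change. For DOR and TTP, a patient who started new anti-cancer therapy may already be censored. For primary PFS, Table 20 ignores new therapy, so a later undated death without documented progression is still affected.

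**4. Size by hand.** Assumptions, not from the documents: all 29 events observed, and a 3-month Kaplan-Meier estimate of 0.50. Changing one event before 3 months to censoring at the same time, with *r* patients at risk, removes a factor (1 − 1/*r*). The estimate rises by 0.50/(*r* − 1).

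- First event, *r* = 29: 0.50/28 = 0.018.
- Event near the median, *r* = 16: 0.50/15 = 0.033.

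About half of patients have their event before 3 months. For the rest, this change leaves the 3-month estimate where it was. The average over a randomly chosen patient is therefore roughly half of 2 to 3 points, that is, a little over 1 point.

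**5. Size by simulation.** Assumptions: n = 29, exponential PFS with a 3-month median, one affected patient chosen at random, last contact uniform over the 0 to 6 weeks before death.

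- Mean change in 3-month PFS when censored at last contact: about +1.0 point (5th to 95th percentile about −0.2 to +2.8). It was unchanged in about 45% of data sets and lower in about 5%.
- Mean change with an event at last contact + 1 day: about −0.2 to −0.3 point, because the imputed date is early.

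A second simulation added administrative censoring at 12 months and affected 0, 1, 2 or 3 patients. Mean 3-month PFS was 49.9%, 50.8%, 52.3% and 53.5%; the mean Kaplan-Meier median was 3.07, 3.17, 3.28 and 3.41 months. That is about 0.1 month per affected patient.

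**The case against.** The strongest case is practical. To be affected, a patient must be known dead with not even the year of death recorded, and must have no earlier documented progression. Patients without progression are imaged every 6 weeks (Protocol 6.2.1 and 10.1.6), and sites must try to establish the vital status of those who do not return (Protocol 10.3.4). PFS, DOR and TTP are secondary and descriptive; ORR, the dose selection and the 7-of-29 rule do not use them. All of this stands. Still, Protocol 10.3.4 sends sites to families, physicians and registries, and such sources can report a death without a date.

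A second objection is that Table 20 needs a date of death, so for an undated death SAP 2.5.3 is the only text a programmer can follow. That is largely right. A reader might infer that the result simply depends on which section is programmed, but the documents do not support that. The firmer complaint is that the one operative sentence contradicts the event definitions and the SAP's own statement of where the censoring rules sit.

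Three further readings are tempting and go too far.

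- *The rule always lengthens PFS and DOR.* It does not. Prior progression leaves the result unchanged. Last contact cannot follow death, so censoring there takes the patient out of the risk set early and can lower an estimate.
- *One case moves 3-month PFS by 2.3 points.* That size appears only if the affected event is forced to fall before 2.5 months, so that it must count at 3 months.
- *The rule wrongly credits time after the last scan.* So does every death event without prior progression, including one at last contact + 1 day. This is not a separate defect.

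**Conclusion.** The point holds in a limited form. For a known death with a wholly missing date and no earlier documented progression, SAP 2.5.3 contradicts the PFS and DOR definitions and Table 20, and contradicts TTP when the death is from progression. It applies a censoring date found in none of these definitions, and it reverses the treatment of partly missing death dates. For DOR and TTP, it matters only if new anti-cancer therapy has not already censored the patient.

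The bias is upward on average: about 1 percentage point on 3-month PFS, or about 0.1 month on the median, per randomly affected patient. Both figures rest on the assumed 29 patients, 3-month exponential median and short gap between last contact and death, none of which the documents supply. The number of such patients is unknown and probably small. A reader should not infer a threat to the trial's main conclusions: the primary endpoint is untouched. This is a minor correction, worth making because the rule as written is wrong and the repair is cheap.

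**What to change.** Replace the last death-date rule in SAP 2.5.3 with, for example:

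*If the death date is completely missing and no progression was documented earlier, the patient is an event for PFS and DOR (and for TTP if death is due to disease progression) at the date of last contact + 1 day, subject to each endpoint's rules on post-treatment anti-cancer therapy; a sensitivity analysis censors at the last valid tumor assessment.*

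Add a matching note to Table 20 so that the two places agree. Other repairs are defensible; what matters is one stated rule that fits the endpoint definitions.

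The cost is one SAP sentence, one programming condition and a small sensitivity analysis, with no new data and no change to the sample size. The downside is that the event date is approximate and may be early, perhaps by a long way when even the year is unknown. The SAP already accepts approximate dates of this kind for partly missing death dates.
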